9.2 Key Secondary Efficacy Endpoint

The key secondary efficacy endpoint is the change from baseline to Day 43 in the CGI-S score.

9.2.1 Key Secondary Analysis

The key secondary efficacy endpoint will be tested using the same hypothetical estimand strategy as for the primary efficacy endpoint.

The data to be included in the key secondary efficacy analysis will be decided by the intercurrent events as described in Table 9-3.

Based on the key secondary hypothetical estimand strategy which assumes patients are on treatment up to the Day 43 assessment, efficacy data collected after discontinuing study treatment (ie, performed more than 3 days after last dose of study treatment) or after starting new ADT will be set to missing and will not be included in the key secondary analysis. Instead, the missing data are assumed as missing at random.

The key secondary efficacy endpoint will be analyzed using an MMRM method similar to the one specified for the primary efficacy endpoint while substituting MADRS total-score-related variables in the model with the corresponding CGI-S-related ones, such as baseline score and visit-by-baseline score interaction.

Confidential Page 26 of 72

_	

Confidential Page 27 of 72

Confidential Page 28 of 72

10. SAFETY ANALYSES

Safety analyses will be performed using the Safety Population. The safety parameters will include AEs, clinical laboratory, vital signs, ECG, and EPS (AIMS, BARS, and SAS) and C-SSRS scales. The baseline for each safety endpoint is defined as the last measurement prior to the first dose of randomized treatment.

10.1 Adverse Events

Adverse events will be coded by system organ class (SOC) and preferred term using the latest version of the Medical Dictionary for Regulatory Activities (MedDRA).

An AE will be considered a treatment-emergent AE (TEAE) if it was not present before the first dose of double-blind study treatment or was present before the first dose of double-blind study treatment but increased in severity after the first dose. An AE that occurs more than 1 day after the date of the last dose of double-blind study treatment will not be counted as a TEAE.

The number and percentage of patients reporting TEAEs in each treatment group will be tabulated by SOC and preferred term; by SOC, preferred term, and severity; and by SOC, preferred term, and relationship to study treatment. If more than one AE is coded to the same preferred term for the same patient, the patient will be counted only once for that preferred term using the most severe and most related occurrence for the summary by severity and by relationship to study treatment.

The incidence of common (\geq 5% of patients in either treatment group) TEAEs will be summarized by preferred term and treatment group.

The number and percentage of patients reporting serious AEs (SAEs) in each treatment group during double-blind treatment period will be tabulated by SOC and preferred term. Also, the number and percentage of patients reporting AEs leading to drug withdrawal in each treatment group will be tabulated by SOC and preferred term. Listings will be presented for patients with SAEs, patients with AEs leading to drug withdrawal, and patients who died (if any).

The incidence of extrapyramidal symptom (EPS) TEAEs will be summarized by preferred term and treatment group and will be sorted by decreasing frequency for lumateperone 42 mg group. The PTs for EPS will be based on broad and narrow Standardised MedDRA Queries (SMQs) as listed in Table 10-1. The analysis for EPS TEAEs based on Broad SMQs will also include the preferred terms listed under Narrow SMQs.

Confidential Page 29 of 72

Table 10-1: Preferred Terms for Extrapyramidal Symptoms

Scope	Preferred Terms		
Narrow	Akathisia, Athetosis, Ballismus, Buccoglossal syndrome, Chorea, Choreoathetosis,		
	Dopamine, dysregulation syndrome, Dyskinesia, Dyskinesia neonatal, Dyskinesia		
	oesophageal, Grimacing, Oculogyric crisis, Pharyngeal dyskinesia, Protrusion tongue,		
	Rabbit syndrome, Respiratory dyskinesia, Tardive Dopa-responsive dystonia, Dystonia,		
	Dystonic tremor, Early onset primary dystonia, Emprosthotonus, Meige's syndrome,		
	Oculogyric crisis, Opisthotonus, Oromandibular dystonia, Pharyngeal dystonia,		
	Pleurothotonus, Spasmodic dysphonia, Torticollis, Trismus, Writer's cramp, Akinesia,		
	Bradykinesia, Cogwheel rigidity, Freezing phenomenon, Hypertonia, Hypertonia neonatal,		
	Hypokinetic dysarthria, Muscle rigidity, On and off phenomenon, Parkinsonian crisis,		
	Parkinsonian gait, Parkinsonian rest tremor, Parkinsonism, Parkinsonism hyperpyrexia		
	syndrome, Parkinson's disease, Parkinson's disease psychosis, Propulsive gait, Resting		
	tremor.		
Broad	All preferred terms listed under Narrow (above) plus the following:		
	Extrapyramidal disorder, Hyperkinesia, Hyperkinesia neonatal, Motor dysfunction,		
	Movement disorder, Psychomotor hyperactivity, Restlessness, Abnormal involuntary		
	movement scale, Chronic tic disorder, Complex tic, Drooling, , Muscle twitching,		
	Provisional tic disorder, Secondary tic, Tic, Blepharospasm, Facial spasm, Gait inability,		
	Laryngospasm,, Muscle contractions involuntary, Muscle spasms, Muscle spasticity, Muscle		
	tightness, Muscle tone disorder, Musculoskeletal stiffness, Oesophageal spasm,		
	Oropharyngeal spasm, Posture abnormal, Posturing, Provisional tic disorder, Risus		
	sardonicus, Tongue spasm, Torticollis psychogenic, Uvular spasm, Action tremor,		
	Bradyphrenia, Dysphonia, Fine motor skill dysfunction, Gait disturbance, Hypokinesia,		
	Hypokinesia neonatal, Laryngeal tremor, Micrographia, Mobility decreased, Postural reflex		
	impairment, Postural tremor, Reduced facial expression, Tremor, Tremor neonatal, Walking		
	disability.		

10.2 Clinical Laboratory Parameters

Descriptive statistics for clinical laboratory values (in International System of units [SI] and conventional units) and changes from baseline values at each assessment visit and at the end of double-blind treatment period will be summarized by treatment group for the following clinical laboratory parameters:

- **Hematology:** hematocrit; hemoglobin; red blood cell count with indices (mean corpuscular volume, mean corpuscular hemoglobin, and mean corpuscular hemoglobin concentration); reticulocytes; white blood cell count and differential (neutrophils, lymphocytes, monocytes, eosinophils, and basophils) reported as percent (%) and absolute values; and platelet count.
- Chemistry: albumin; alkaline phosphatase; alanine aminotransferase (ALT); aspartate aminotransferase (AST); bilirubin (total, direct); blood urea nitrogen (BUN); calcium; chloride; cholesterol (high-density lipoprotein [HDL] and low-density lipoprotein [LDL] will be calculated and reported); creatinine; creatine phosphokinase; gamma-glutamyl transferase; glucose; insulin; lactate dehydrogenase; phosphate; potassium; prolactin; sodium; triglycerides; total protein; uric acid; HbA1c; and thyroid-stimulating hormone (TSH) (reflex free T3 and free T4).
- Urinalysis: pH and specific gravity.

Confidential Page 30 of 72

Clinical laboratory values are considered potentially clinically significant (PCS) values if they meet either the lower or upper criteria listed in Table 10-2. The number and percentage of patients with PCS postbaseline clinical laboratory values during double-blind treatment period will be tabulated by treatment group. The percentages will be calculated relative to the number of patients with available non-PCS baseline values and at least 1 postbaseline assessment. The numerator will be the total number of patients with available non-PCS baseline values and at least 1 PCS postbaseline value. A supportive listing of patients who have PCS values will be provided and will include the PID number and baseline and postbaseline values for each patient. A listing of all AEs for patients with PCS clinical laboratory values will also be provided.

Confidential Page 31 of 72

Table 10-2: Criteria for Potentially Clinically Significant Clinical Laboratory Tests

Laboratory Parameter	Conventional Unit	PCS Criteria ^a Low Values	PCS Criteria ^a High Values
Hematology			
Hemoglobin	g/dL	< 0.9 × LLN	_
Hematocrit	%	< 0.9 × LLN	_
Absolute neutrophil count (ANC)	$10^3/\mu L$	< 1.0	_
Platelet count	$10^3/\mu L$	≤ 75	≥ 700
White blood cell (WBC) count	$10^3/\mu L$	≤ 2.5	≥ 15
Chemistry			•
Albumin	g/dL	< 2.5	_
Alkaline phosphatase	U/L	_	≥2×ULN
ALT	U/L	_	\geq 3 × ULN
AST	U/L	_	\geq 3 × ULN
BUN	mg/dL	_	≥ 30
Calcium	mg/dL	< 7	> 12
Chloride	mEq/L	< 90	> 115
Total Cholesterol	mg/dL	_	≥ 300
СРК	U/L	_	≥ 5 × ULN
Creatinine	mg/dL	_	> 1.3 × ULN
Glucose	mg/dL	< 45	> 160
LDL Cholesterol	mg/dL	_	> 200
Potassium	mEq/L	< 3	> 5.5
Prolactin	ng/ml	_	> 200
Sodium	mEq/L	< 130	> 150
Total bilirubin	mg/dL	_	≥ 2 × ULN
Total protein	_	< 0.9 × LLN	> 1.1 × ULN
Triglycerides	mg/dL	_	≥ 300
Uric Acid	mg/dL	_	> 1.1 × ULN
Urinalysis			
Protein	_	_	At least 2 +
Glucose	_	_	At least 2 +
Blood			At least 2 +

a Criteria refer to conventional units.

ALT = alanine aminotransferase; AST = aspartate aminotransferase; BUN = blood urea nitrogen; CPK=creatine phosphokinase; LLN = lower limit of normal of laboratory reference range; PCS = potentially clinically significant; ULN = upper limit of normal of laboratory reference range.

Confidential Page 32 of 72

The number and percentage of patients with shifts from baseline at the end of double-blind treatment period according to normal range and PCS criteria (PCS Low, Low, Normal, High, PCS High) will be provided if applicable.

The criteria for elevated liver function-related laboratory values are specified in Table 10-3. The frequency and percentage of subjects with treatment-emergent elevated liver function values during the double-blind treatment period will be summarized for each treatment group for the Safety Population.

Table 10-3: Elevated Liver Function Criteria

Liver Function Parameter	Criteria	
	≥ 3 × ULN	
ALT	≥ 5 × ULN	
ALI	$\geq 10 \times ULN$	
	$\geq 20 \times ULN$	
	$\geq 3 \times ULN$	
AST	$\geq 5 \times ULN$	
ASI	$\geq 10 \times ULN$	
	$\geq 20 \times ULN$	
ALT or AST	\geq 3 × ULN	
	$\geq 5 \times ULN$	
	$\geq 10 \times ULN$	
	\geq 20 × ULN	
Total Bilirubin	$\geq 1.5 \times ULN$	
	$\geq 2 \times ULN$	
Alkaline phosphatase	≥ 1.5 × ULN	
	≥2×ULN	
Combined Elevation in ALT or AST, and	ALT or AST \geq 3 × ULN, Total Bilirubin \geq 1.5 × ULN	
Total Bilirubin	ALT or AST \geq 3 × ULN, Total Bilirubin \geq 2 × ULN	
Hy's Law	Concurrent evaluation ^a : ALT or AST \geq 3 × ULN, Total Bilirubin \geq 2 × ULN, and Alkaline phosphatase $<$ 2 × ULN	

a Concurrent assessments: analytes may come from multiple samples taken within a 24-hour period. ALT = alanine aminotransferase; AST = aspartate aminotransferase; ULN = upper limit of normal of laboratory reference range.

10.3 Vital Signs

Descriptive statistics for vital signs (eg, supine pulse rate, supine systolic and diastolic BP, body weight) values at baseline and changes from baseline values at each assessment visit, and at the end of the treatment period will be presented by treatment group.

Confidential Page 33 of 72

Vital sign values will be considered PCS if they meet the criteria for both the observed value and the change from baseline value listed in Table 10-4. The number and percentage of patients with PCS postbaseline vital sign values during double-blind treatment period will be tabulated by treatment group for the Safety Population. The percentages will be calculated relative to the number of patients with an available baseline value and at least 1 postbaseline assessment. The numerator will be the total number of patients with an available baseline value and at least 1 PCS postbaseline vital sign value. A supportive listing of patients with PCS postbaseline values will be provided and will include the PID number and baseline and postbaseline values for each patient. A listing of all AEs for patients with PCS vital sign values will also be provided.

Table 10-4: Criteria for	rotentiany Chin	icany Significan	t vitai Signs

Viv. I Gi B	Flag	Criteria ^a	
Vital Sign Parameter, unit		Observed Value	Change From Baseline
Suning Systelia blood prossure mm Ha	High	≥ 180	Increase of ≥ 20
Supine Systolic blood pressure, mm Hg	Low	≤ 90	Decrease of ≥ 20
Supine Diastolic blood pressure, mm Hg	High	≥ 105	Increase of ≥ 15
	Low	≤ 50	Decrease of ≥ 15
Cuning Dulga rata ham	High	≥ 120	Increase of ≥ 15
Supine Pulse rate, bpm	Low	≤ 50	Decrease of ≥ 15
W. 14b	High	_	Increase of ≥ 7%
Weight ^b	Low	_	Decrease of ≥ 7%

a A postbaseline value will be considered potentially clinically significant if it meets both criterion value and change from baseline.

bpm = beats per minute.

The number and percentage of patients with post-baseline orthostatic hypotension (OH) will be provided by treatment group for the Safety Population. OH is defined as a reduction of ≥ 20 mm Hg in SBP or a reduction of ≥ 10 mm Hg in DBP while changing from the supine to standing position. A supportive listing of patients with OH will be provided. A listing of all AEs occurring in patients who experienced OH will also be provided.

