10.4 Electrocardiograms

Descriptive statistics for ECG parameters (eg, ventricular heart rate, QTc interval, QRS interval) at baseline and changes from baseline values at each assessment visit, and at the end of the double-blind treatment period will be summarized by treatment group.

ECG parameter values will be considered PCS if they meet the criteria listed in Table 10-5. The number and percentage of patients with PCS postbaseline values during double-blind treatment period will be tabulated by treatment group for the Safety Population. The percentages will be calculated relative to the number of patients with baseline value (for criteria involving change from baseline) or non-PCS baseline value (for criteria not involving change from baseline), and at least 1 assessment during the double-blind treatment period. The numerator will be the total number of

Confidential Page 34 of 72

b Weight change is relative to baseline.

patients out of those included in the denominator and with at least 1 PCS value during the double-blind treatment period. A supportive listing for all patients with PCS values will be provided, which will include the PID number and baseline and postbaseline ECG values for each patient. A listing of all AEs for patients with PCS ECG values will also be provided.

Table 10-5. Criteria for Potentially Clinically Significant Electrocardiographic Values

D	Criteria ^a			
Parameter, unit	Value	Change from Baseline		
QRS duration, msec	≥ 150	_		
PR interval, msec	≥ 250	_		
QTcB, msec	≥ 480	_		
QTcB, msec	≥ 500	_		
QTcF, msec	≥ 480	_		
QTcF, msec	≥ 500	_		
QTcB, msec	_	Increase of > 30 and ≤ 60		
QTcB, msec	_	Increase of > 60		
QTcF, msec		Increase of > 30 and ≤ 60		
QTcF, msec	_	Increase of > 60		

a A post-baseline value will be considered potentially clinically significant if it meets the criterion value or the change from baseline value.

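### The orthostatic hypotension table does not separate patients who already had it before the first dose from new cases, which dilutes the drug-placebo ratio

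*SAP*

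**What the plan says.** SAP 10.3 says: "The number and percentage of patients with post-baseline orthostatic hypotension (OH) will be" provided by treatment group for the Safety Population. The definition follows: "OH is defined as a reduction of ≥ 20 mm Hg in SBP or a reduction of ≥ 10 mm Hg in DBP" on moving from lying to standing. This compares two readings at one visit and has no change-from-baseline part. The section also plans a listing of patients with OH and a listing of their adverse events. It does not say who belongs in the percentage denominator. The PCS (potentially clinically significant) vital-sign sentence in the same section is limited to the double-blind treatment period, but the OH sentence is not.

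Three other rules in the SAP do take account of baseline:

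- Laboratory PCS values (SAP 10.2): "The percentages will be calculated relative to the number of patients with available non-PCS baseline values and at least 1 postbaseline assessment".
- ECG PCS values (SAP 10.4): the denominator requires a "non-PCS baseline value (for criteria not involving change from baseline"). OH is a criterion of this kind.
- Vital-sign PCS values (SAP 10.3): "Vital sign values will be considered PCS if they meet the criteria for both the observed value and the change from baseline value". OH is not among the criteria in Table 10-4.

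Protocol 8.3.5 has blood pressure taken lying and then standing, with vital signs at every visit. SAP 10 defines the safety baseline as the last measurement before the first dose. Protocol 9.4.7.3 gives no OH rule and leaves further vital-sign analyses to the SAP.

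**The concern.** No exclusion criterion in protocol 6.3.2 names OH, and stable treated hypertension is allowed, so patients can enter with OH already present. If such a patient has a qualifying drop at any later visit, the table counts that patient exactly like someone who developed OH on treatment.

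These recurrent cases are expected in both arms in similar numbers. They raise both percentages and make any relative increase on lumateperone look smaller than it is among patients who started without OH. In a safety table, dilution towards no difference is the less cautious direction. Baseline status can be derived from data already collected, so nothing in the design forces this.

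**Working it through.** The documents state no OH rate, count or power, so there is no plan figure to reproduce. What follows is an illustration.

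**Inputs**

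- n = 235 per arm (protocol synopsis and 9.2).
- b = proportion with OH at baseline. Assumed 2%, 5%, 10%.
- r = probability that a patient with baseline OH shows it again after baseline, taken as equal in both arms. Assumed 0.5, with 0.8 as a variant.
- q = risk of new-onset OH among patients free of it at baseline. Assumed 5% on placebo and 10% on lumateperone, so the true ratio is 2.00 and the true difference 5.0 points.

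**Formulas**

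- Expected proportion counted under the SAP rule: b·r + (1−b)·q.
- Pre-existing cases counted per arm: 235·b·r.
- After restriction to patients without baseline OH: q, in about 235·(1−b) patients per arm.

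**Results at r = 0.5**

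| b | Placebo, SAP rule | Lumateperone, SAP rule | Ratio | Pre-existing cases per arm | Patients per arm after restriction |
|---|---|---|---|---|---|
| 2% | 0.010 + 0.049 = 5.9% | 0.010 + 0.098 = 10.8% | 1.83 | 235 × 0.010 = 2.4 | 230 |
| 5% | 0.025 + 0.0475 = 7.25% | 0.025 + 0.095 = 12.0% | 1.66 | 235 × 0.025 = 5.9 | 223 |
| 10% | 0.050 + 0.045 = 9.5% | 0.050 + 0.090 = 14.0% | 1.47 | 235 × 0.050 = 11.8 | 212 |

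Restriction returns 5% versus 10% and a ratio of 2.00 in every row.

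**Variant.** There are six scheduled post-baseline treatment visits, and OH at any one of them counts, so r could exceed 0.5. For example, an assumed 30% chance per visit, independent across visits, gives 1 − 0.7^6 = 88%. At r = 0.8 the ratios for b = 2%, 5% and 10% are 1.75, 1.54 and 1.36.

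**Risk difference.** Recurrent cases cancel, leaving (1−b)·5.0 points: 4.9, 4.75 and 4.5. The absolute difference is barely affected.

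**Noise from chance imbalance.** Take 5% new-onset OH in both arms and r = 0.5. The SD of the between-arm difference is √(2p(1−p)/n).

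- SAP rule, n = 235, p = 5.9%, 7.25%, 9.5%: 2.17, 2.39, 2.70 points.
- After restriction, p = 5%, n = 235·(1−b): 2.03, 2.06, 2.12 points.
- Increase: 0.14, 0.33, 0.59 points. If every baseline case recurred, it would be 0.31, 0.67, 1.13 points.

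**The case against.** The strongest reply is that the table is what it claims to be. It is labelled post-baseline OH, it is descriptive, and no test or decision depends on it. A count of everyone with OH during follow-up is a legitimate summary. OH is not called PCS, so no stated rule is broken. This stands: the point is an improvement and does not correct a contradiction.

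A reader might go further in three ways that the documents do not support.

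- *That OH is the one exception to a uniform rule.* The SAP uses several conventions. The C-SSRS section (SAP 10.5.4) first tabulates ideation and behavior in the double-blind period without removing baseline cases, and adds emergence separately. Protocol 9.4.7.2 states no baseline exclusion for its Hy's law count. The fair comparison is with the laboratory rule and the ECG rule for absolute values.
- *That all baseline cases enter the count, and that their imbalance is the added noise.* At 2%, 5% and 10% prevalence, about 5, 12 and 24 patients per arm would have OH at entry, but only those who show it again are counted. The SD of the between-arm difference in baseline prevalence, √(2b(1−b)/235) = 1.3, 2.0 and 2.8 points, is likewise not the noise added to the OH comparison, which is much smaller.
- *That the table could produce a false drug signal.* Randomisation balances baseline OH in expectation. Only chance imbalance could do this, and it adds little.

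Two further objections have some weight. Excluding patients with baseline OH would hide any whose OH worsens, and would rest on one baseline reading. The fix below keeps those patients visible. Separately, SAP 2 says that table specifications sit in another document, which might define the denominator or show baseline status. That is unknown. The planned OH listings and adverse-event tables do not give the split: the SAP does not say that the OH listing shows baseline readings, as the PCS vital-sign listing must.

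**Conclusion.** The point holds as a minor one. SAP 10.3 mixes recurrent pre-existing OH with new OH and leaves the percentage denominator undefined, although the data to separate the two are collected. The expected effect is inflated rates in both arms and a ratio pulled towards 1. At an assumed 2% to 10% baseline prevalence, 50% recurrence equal in both arms and new-onset OH of 5% versus 10%, a true ratio of 2.00 would appear as about 1.83 to 1.47, with about 2 to 12 pre-existing cases counted per arm of 235. The risk difference is nearly unchanged, and the extra noise is about 0.1 to 0.6 points when new-onset OH is 5% in both arms. All these rates are assumptions, so the real size is unknown and could be negligible if baseline OH is rare.

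**What to change.** In SAP 10.3, add treatment-emergent OH during the double-blind treatment period:

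- Denominator: Safety Population patients with a baseline supine/standing pair, no OH at baseline, and at least one post-baseline pair.
- Numerator: those among them with OH at any post-baseline visit in that period.

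Keep the all-patient post-baseline count beside it, or add a baseline-by-post-baseline OH shift table, so that patients with OH at entry remain visible. State the denominator and period for the all-patient count too.

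The cost is one or two sentences in the SAP, one extra table row and a slightly smaller denominator (about 230 to 212 per arm at the assumed prevalences). No new data are needed.

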10.4 Electrocardiograms

Descriptive statistics for ECG parameters (eg, ventricular heart rate, QTc interval, QRS interval) at baseline and changes from baseline values at each assessment visit, and at the end of the double-blind treatment period will be summarized by treatment group.

ECG parameter values will be considered PCS if they meet the criteria listed in Table 10-5. The number and percentage of patients with PCS postbaseline values during double-blind treatment period will be tabulated by treatment group for the Safety Population. The percentages will be calculated relative to the number of patients with baseline value (for criteria involving change from baseline) or non-PCS baseline value (for criteria not involving change from baseline), and at least 1 assessment during the double-blind treatment period. The numerator will be the total number of

Confidential Page 34 of 72

b Weight change is relative to baseline.

patients out of those included in the denominator and with at least 1 PCS value during the double-blind treatment period. A supportive listing for all patients with PCS values will be provided, which will include the PID number and baseline and postbaseline ECG values for each patient. A listing of all AEs for patients with PCS ECG values will also be provided.

Table 10-5. Criteria for Potentially Clinically Significant Electrocardiographic Values

D	Criteria ^a			
Parameter, unit	Value	Change from Baseline		
QRS duration, msec	≥ 150	_		
PR interval, msec	≥ 250	_		
QTcB, msec	≥ 480	_		
QTcB, msec	≥ 500	_		
QTcF, msec	≥ 480	_		
QTcF, msec	≥ 500	_		
QTcB, msec	_	Increase of > 30 and ≤ 60		
QTcB, msec	_	Increase of > 60		
QTcF, msec		Increase of > 30 and ≤ 60		
QTcF, msec	_	Increase of > 60		

a A post-baseline value will be considered potentially clinically significant if it meets the criterion value or the change from baseline value.

